## 2.2 Study Design

### 2.2.1 Overview

This is a multi-site, open-label, randomized, parallel arm, Phase 1/2 adaptive study to evaluate the efficacy and safety of ANV419 as a monotherapy and in combination with pembrolizumab or ipilimumab in patients aged 18 years or older with advanced cutaneous melanoma who have previously been treated with at least 1 line of standard of care immunotherapy, including an anti-PD-1/anti-PD-L1 antibody.

The 4 following treatment arms will be included in this study:

- Arm A1: [REDACTED]
- Arm A2: [REDACTED]
- Arm B: ANV419 [REDACTED] in combination with pembrolizumab
- Arm C: ANV419 [REDACTED] in combination with ipilimumab

[figure not shown]
There will be up to 3 separate parts in this study:

Part 1: Monotherapy Dose Expansion with patients randomized to receive infusion of ANV419

Part 2: Combination Dose Finding with patients randomized to Arms B and C with infusion of ANV419 [REDACTED] Part 2 will open if part 1 is successful.

Part 3: Combination Dose Expansion with patients randomized to Arms B and C (see Figure 2-1). Part 3 will open if part 2 is successful.

Figure 2-1: Study Design

\* = If ANV419 monotherapy is successful, the combination portion will be initiated.

\*\* = Dose escalation increment is decided by the SRC until RP2D of ANV419 per arm is identified.

\*\*\* = Arm not meeting pre-specified ORR criteria may be stopped early after Stage 1.

In the Combination Dose Finding part, patients will be manually randomized to Arm B or Arm C. In the Monotherapy Dose Expansion part and the Combination Dose Expansion part, patients will be randomized by IRT into Arms A1 or A2 and Arms B or C, respectively.

Ipi = ipilimumab; IRT = Interactive Response Technology; ORR = objective response rate; Pembro = pembrolizumab; R = randomization; RP2D = recommended Phase 2 dose; SRC = Safety Review Committee.

### 2.2.1.1 Part 1: Monotherapy Dose Expansion

The Monotherapy Dose Expansion part (Arms A1 and A2) will be a parallel group part with a Bayesian sequential monitoring analysis and up to 15 patients per arm. This part will establish the efficacy and safety of ANV419 as monotherapy.

All responses will be assessed locally using RECIST 1.1 and used for decision making. There is 95% certainty that the true objective response rate (ORR) is greater than 10% if we observe any 1 of the following.

- 2 responses in 3 to 7 patients

- 3 responses in 8 to 13 patients
- 4 responses in 14 to 19 patients
- 5 responses in 20 to 27 patients

#### 2.2.1.2 Part 2: Combination Dose Finding

This part will be initiated when at least 2 responses have been observed in the Monotherapy Dose Expansion part.

The Combination Dose Finding part will be comprised of 2 arms (Arms B and C) that will identify a recommended Phase 2 dose (RP2D) for ANV419 in each arm when administered in combination with pembrolizumab (Arm B) or ipilimumab (Arm C) at the prescribed dosing. The number of patients recruited to each arm will be between 6 and 25 patients depending on the number of doses increment possible. A minimum of 6 patients will be treated at RP2D. The patients from the Combination Dose Finding part will not be randomized into the Combination Dose Expansion part.

Dosing of ANV419 when administered in combination with pembrolizumab (Arm B) or ipilimumab (Arm C) will occur as shown in Table 2-4, with a dose of ANV419 currently planned to start at [REDACTED]

[REDACTED] Patients in the Combination Dose Finding part will be treated with a minimum of 24 hours interval between patients to allow for monitoring of acute toxicities. Dose level 1, as shown in Table 2-4 will be reviewed by the Safety Review Committee (SRC) per the safety evaluations and the SRC will make dose increment recommendations at each dose level, not exceeding 3-fold increment from one dose level to the next. The maximum dose level explored will not exceed the [REDACTED] studied in the ongoing ANV419-001 study.

Table 2-4: ANV419 Dose Escalation Plan for Combination Dose Finding Part (Pembrolizumab or Ipilimumab)

Dose Level	ANV419 Dose	Pembrolizumab Dose or Ipilimumab Dose	Frequency
1	[REDACTED]	[REDACTED]	[REDACTED]
2	[REDACTED]	[REDACTED]	[REDACTED]
3	[REDACTED]	[REDACTED]	[REDACTED]
4	[REDACTED]	[REDACTED]	[REDACTED]
5	[REDACTED]	[REDACTED]	[REDACTED]

Note: ANV419 will be administered by IV infusion over 15 minutes (+5 minutes).

1. Dose increments will be determined by the SRC based on a synthesis of all relevant data available from all dose levels evaluated in this study, not exceeding a 3-fold increment from one dose level to the next. The maximum dose level explored will not exceed the Q3W dose of ANV419 monotherapy studied in the ongoing ANV419-001 study.

IV = intravenous(ly); [REDACTED] SRC = Safety Review Committee; TBD = to be determined.

Dose escalation in the Combination Dose Finding part will follow the Bayesian optimal interval (BOIN) design to find the maximum tolerated doses (MTDs)/RP2D of ANV419 when administered in combination with pembrolizumab or ipilimumab at the prescribed dose. Dose escalation decisions will be based on a synthesis of all relevant data available from all dose levels evaluated in the ongoing Combination Dose Finding part of the study.

### 2.2.1.3 Part 3: Combination Dose Expansion

The Combination Dose Expansion part of the study will be separate from the Combination Dose Finding part and will further evaluate the safety and efficacy of ANV419 in combination with pembrolizumab (Arm B) or ipilimumab (Arm C). This Combination Dose Expansion part will consist of 2 stages. In Stage 1, 12 patients will be randomized by interactive response technology (IRT) into each arm. At the end of this stage, an interim analysis will be performed to assess continuation of treatment arms into Stage 2 (see Table 2-5). In Stage 2, eligible patients will be randomized to the remaining treatment arms, determined at the interim analysis. Recruitment will continue until 25 patients have been randomized to a treatment arm.

Table 2-5: Continuation Decision Rules for Combination Dose Expansion Part

Treatment Arm Accrual	Discontinue if the Number of Responses is	Discontinue Criterion in Terms of ORR	Continue if the Number of Responses is at Least
Stage 1 (n=12)	≤2	Observed ORR <20%	3

ORR = objective response rate.

Treatment with ANV419 in combination with ipilimumab can continue up to a maximum [REDACTED] per the approved label (United States Prescribing Information and Summary of Product Characteristics). If ipilimumab-related AEs occur, ipilimumab can be discontinued at any time. Once a patient has completed the maximum [REDACTED] of ipilimumab allowed, they will continue receiving ANV419 at the dose enrolled as [REDACTED] in the absence of disease progression or unacceptable toxicity.

### 2.2.2 Randomization and Blinding

#### Part 1: Monotherapy Dose Expansion

Patients will be randomized by IRT and stratified by locally assessed BRAF mutation status into Arms A1 or A2 on Cycle 1 Day 1.

#### Part 2: Combination Dose Finding part

Patients will be manually randomized into Arm B or Arm C on Cycle 1 Day 1. Steps for assigning the randomization number are as follows: The Clinical Operations team/trained individuals will use the pre-generated randomization number lists to find the next available randomization number and assign it to the patient. The team will then use the randomization number to obtain the treatment assignment from the pre-generated randomization scheme provided by the Biostatistics team. The Clinical Operations team will maintain and complete the randomization schemes throughout the course of study.

#### Part 3: Combination Dose Expansion part

Patients enrolled in the Combination Dose Expansion part will be randomized by IRT and stratified by BRAF mutation status into Arms B or C on Cycle 1 Day 1. For the Combination Dose Expansion part, following the interim analysis at the end of Stage 1, if 1 treatment arm is removed from Stage 2 (leaving only 1 treatment arm open for enrollment), randomization by IRT will no longer be required and eligible patients will be enrolled into the remaining treatment arm, provided there are sufficient slots remaining.

This is an open-label study. No blinding is required.

### 2.2.3 Study Drug

ANV419 is a stable fusion protein comprised of IL-2 fused to an anti-IL-2 mAb that sterically blocks the binding of the IL-2 to IL-2R-alpha (CD25). The ANV419 investigation product is a liquid, colorless, clear formulation with no visible particles, containing 2.5 mg/mL ANV419 protein, 20 mM histidine, 8% (w/v) sucrose, and 0.02% (w/v) PS80, pH 6.0. ANV419 is stored at -20°C (±5°C) and thawed by leaving at room temperature (15°C to 25°C) for approximately 1 hour and then further diluted into normal saline.

Patients will receive ANV419 as monotherapy (Arms A1 and A2) or in combination with pembrolizumab (Arm B) or ipilimumab (Arm C) after all Screening procedures have been completed and eligibility has been confirmed by the Investigator. Only patients enrolled in the study may receive the study drug(s). Under no circumstances will the study drug(s) be used other than as directed within this Protocol. The 3 study drugs and the administration of each are described in Table 2-6.

Table 2-6: Study Drug Administration

Treatment	Study Part	Arm	Dose/ Potency	Dose Frequency	Route Administration/Duration of	Regimen/ Treatment Period
ANV419						
Pembrolizumab						
Ipilimumab Error! Reference source not found., Error! Reference source not found.						

### 2.2.4 Sample Size Determination

#### Part 1: Monotherapy Dose Expansion

This part of the study will use Bayesian sequential monitoring. A maximum of 15 patients will be enrolled and treated in each arm. A1 and A2 monotherapy arms will be analyzed as independent experiments, and overall, and the following assumptions are made:

- Nothing is known *a priori*: assume a uniform prior, i.e., the true ORR could be any value between 0% and 100%;
- A true ORR <6% indicates treatment failure; and
- A true ORR >10% indicates treatment success.

With a maximum of 15 patients in each arm, if no responses are observed, then the estimated true ORR would be 5.9%, with 90% confidence interval (CI) of 0.3% and 17.1% respectively. This would be sufficient evidence to suggest that the treatment is not clinically meaningful unless clinical benefit is demonstrated with other means (i.e., durable SDs > 6 months). With a maximum of 30 patients overall, if no responses were observed, then the estimated true ORR would be 3.1%, with 90% CI (0.2%, 9.2%). This would be sufficient evidence to suggest that the treatment at either dose is not clinically meaningful.

There is 95% certainty that the true ORR is greater than 10% if any of the following scenarios are observed:

- 2 responses in 3 to 7 patients
- 3 responses in 8 to 13 patients
- 4 responses in 14 to 19 patients
- 5 responses in 20 to 27 patients

### Part 2: Combination Dose Finding

The Combination Dose Finding part will employ BOIN to find the MTD/RP2D of Arm B (ANV419 in combination with pembrolizumab) and Arm C (ANV419 in combination with ipilimumab). For each arm, the following assumptions have been predefined for the dose escalation:

1. Target DLT rate of 25%;
2. Maximum of 25 patients;
3. Maximum of 9 patients treated at the same dose level; and
4. Maximum of 5 dose levels defined in **Error! Reference source not found.** to be tested.

Patients will be enrolled and treated in cohorts of 3 patients (at least). Up to 50 patients in total will be enrolled for the Combination Dose Finding part, with a minimum of 6 patients treated at RP2D.

### Part 3: Combination Dose Expansion (efficacy analysis)

The sample size calculation is based on a Simon's 2-stage design and ensures that under all possible distributions of patients to the 2 treatment arms, there is at least 80% power to correctly detect an ORR >40% and at most a Type I error rate of 10% of rejecting a null hypothesis that ORR <20%. This results in a sample size of 12 patients randomized to each treatment arm in Stage 1, followed by 13 additional patients randomized during Stage 2: a total of 25 patients per arm at the end of Stage 2.

### 3 STATISTICAL METHODOLOGY

#### 3.1 General Considerations

##### 3.1.1 *Analysis Day*

Analysis day will be calculated from the date of first dose of study drug. The day of the first dose of the study drug will be Day 1, and the day immediately before Day 1 will be Day -1. There will be no Day 0.

##### 3.1.2 *Definition of Baseline*

Unless stated otherwise, Baseline is defined as the last non-missing measurement prior to the first dose of the study drug.

##### 3.1.3 *Unscheduled Visits*

Unscheduled visits will not be included in by-visit summaries but will contribute to the derivation of best or worst-case values and will be presented in data listings. Visit windowing will not be used for handling unscheduled visits.

##### 3.1.4 *Summary Statistics*

No formal hypothesis testing is planned, and summaries will in general be descriptive. Appropriate summaries will be provided for each assessment based on data type (continuous or categorical).

Categorical data will generally be summarized with number and percentages of patients. The denominator used for the percentage calculation will be clearly defined. Continuous data will generally be summarized with descriptive statistics including n (number of non-missing values), mean, median, standard deviation, minimum, and maximum.

Time-to-event endpoints (progression-free survival, duration of response, and overall survival) will be summarized using Kaplan-Meier methods and 95% confidence interval.

Unless described otherwise, analyses will in general be presented for each arm by treatment arm and BRAF Mutation status (wild-type or BRAFV600) in the Monotherapy Dose Expansion part and by dose level in the Combination Dose Finding part and Combination Dose Expansion part of, and overall using descriptive statistics.

##### 3.1.5 *Handling of Dropouts and Missing Data*

Unrecorded data values will be recorded as missing. Only recorded (i.e., complete) data values will be used for statistical analyses. In general, invalid, or missing values will not be imputed unless stated otherwise.

If needed, completely or partially missing start and end dates for medical history events, including date of initial diagnosis and last date of last progression for the primary cancer history, will be imputed in a conservative fashion as follows:

Date	Type of Missing Date	Handling of Missing Date
Event Start Date (e.g., YYYY-MM-DD)	Completely missing	No imputation will be applied.
	Only YYYY is available	Use the first day of YYYY to impute the missing month and date parts of the start date
	YYYY and MM are available, but DD is missing	Use the first day of MM to impute the missing date part of the start date
Event End Date (e.g., YYYY-MM-DD)	Completely missing	No imputation will be applied. The event will be considered ongoing at the end of study.
	Only YYYY is available	Use the last day of YYYY to impute the missing month and date parts of the end date
	YYYY and MM are available, but DD is missing	Use the last day of MM to impute the missing date part of the end date

For missing or partial AEs and concomitant medications dates, conservative conventions will be applied to assign the events to corresponding periods. AEs will be considered as treatment-emergent, and the medications will be considered as concomitant if the missing/partial dates cannot definitively exclude the treatment period. Handling incomplete dates (e.g., AE, and concomitant medications dates) are described in Table 7-1 and Table 7-2 from [Appendix A](#).

For patients lost to follow-up or with missing RECIST/iRECIST assessments, censoring rules for efficacy endpoints are defined in section 3.4.

## 3.2 Analysis Populations

### 3.2.1 Safety Population

The Safety Population is defined as all patients who receive at least 1 dose (or partial dose) of study drug(s). The Safety Population will be used for safety analyses including DLT assessments during the DLT observation period in part 2.

### 3.2.2 Efficacy Population

The Efficacy Population is defined as all patients who receive at least 1 dose of study drug, have at least 1 post-baseline tumor assessment, and who are part of the Monotherapy Dose Expansion part, Combination Dose Finding part, or the Combination Dose Expansion part. The Efficacy Population will be used for efficacy analyses.

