#### *3.4.1 Best Overall Response (BOR)*

Best Overall Response (BOR) will be determined based on the overall visit responses.

BOR per RECIST v1.1 is defined as the best response in the order of: Complete Response (CR), Partial Response (PR), Stable Disease (SD), Progressive Disease (PD), and Not Evaluable (NE) for patients with measurable disease. The minimum duration of Stable Disease to be considered as the best overall response is 3 weeks from first dose of the study treatment.

iBOR per iRECIST is defined as the best response in the order of: Immune Complete Response (iCR), Immune Partial Response (iPR), Immune Stable Disease (iSD), Immune Confirmed Progression (iCPD), Immune Unconfirmed Progression (iUPD) and NE for patients with measurable disease. The minimum duration of Immune Stable Disease to be considered as the best overall response is 3 weeks from first dose of the study treatment.

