##### *3.4.2.2 Disease Control Rate (DCR)*

Disease control rate (DCR) per RECIST is defined as the proportion of patients whose best overall response is CR, PR, or SD  $\geq$  4 Weeks from first dose.

DCR per iRECIST (iDCR) is defined as the proportion of subjects whose best overall response is an iCR, iPR, or iSD  $\geq$  4 Weeks from first dose.

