### 3.4.2.4 Progression Free Survival (PFS)

PFS per RECIST 1.1 will be defined as the time from the first dose date to the earliest date of the first documented PD per RECIST 1.1 assess locally, initiation of alternate anti-cancer therapy, or death due to any cause, whichever occurs first.

PFS per RECIST 1.1 will be calculated as:

$$\text{PFS (months)} = (\text{Event/censoring date} - \text{first dose date of ANV419} + 1) / 30.437$$

For subjects who have not progressed and are still alive at time of data cutoff for study analysis or who are lost to follow-up, PFS will be right censored. The event or censoring date will be determined based on the conventions listed in Table 3-3. .

Table 3-3: Date of Event or Censoring for PFS per RECIST v1.1

Situation	Date of progression or censoring	Outcome
Death or disease progression after one missed tumor assessment	Date of death or first disease assessment showing disease progression	Event
Death or disease progression after missing two or more consecutively scheduled disease assessments	Date of last evaluable disease assessment visit without documentation of disease progression or Date of first dose of study treatment, whichever comes later	Censored
Alive and without disease progression and no initiation of alternate anticancer	Date of last evaluable disease assessment or Date of first dose of study treatment, whichever comes later	Censored
Alive with No (or Non-evaluable) post-baseline disease assessments	Date of the first dose of study treatment	Censored
Initiation of alternate anticancer treatment before disease progression or death (without disease progression beforehand)	Date of last evaluable disease assessment prior to the start of alternate anti-cancer treatment	Censored

iPFS per iRECIST will be defined as the time from the first dose date to the earliest date of the first documented iCPD per iRECIST, initiation of alternate anti-cancer therapy, or death due to any cause, whichever occurs first. If iUPD occurs, but is disregarded because of later iSD, iPR, or iCR, that iUPD date should not be used as the progression event date. In the case of an assessment of iUPD is recorded and no subsequent evaluable iRECIST assessments are recorded, the iUPD event will be treated as confirmed disease progression.

iPFS per iRECIST will be calculated as:

$$iPFS \text{ (months)} = (\text{Event/censoring date} - \text{first dose date of ANV419} + 1) / 30.437$$

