### 3.4.3 Primary Efficacy Endpoints

For Part 1 (Monotherapy Dose expansion) and Part 3 (Combination Dose Expansion), the primary efficacy endpoint is ORR using RECIST 1.1

The point estimates of ORR along with the exact Clopper-Pearson 95% CI will be presented by treatment arm in the Monotherapy Dose Expansion part and Combination Dose Expansion part and overall based on the Efficacy Population.

For Part 2 (Combination Dose Finding), the efficacy analyses are considered as secondary (see Section 3.4.4).

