##### 3.4.4.3 Disease Control Rate

DCR per RECIST v1.1 and iDCR per iRECIST will be analyzed in same manner as ORR.

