#### *3.4.4.5 Progression Free Survival*

Unless specified otherwise, the analytical methods described in Section 3.4.4.3 for DOR/iDOR will be used for PFS/iPFS. PFS/iPFS summaries will be presented based on Safety Population.

In addition, the number and percentages of patients experiencing a PFS/iPFS event, types of events, and patients censored will be summarized.

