#### *3.4.4.6 Overall survival*

Unless specified otherwise, the analytical methods described in Section 3.4.4.3 for DOR will be used for OS. OS summary will be presented based on Safety Population.

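### ORR, best overall response and DCR drop treated patients with no post-baseline scan, while PFS and OS keep them; an all-treated version should be added

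*SAP*

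**What the plan says.** The Efficacy Population in SAP 3.2.2 is "all patients who receive at least 1 dose of study drug, have at least 1 post-baseline tumor assessment", within the study parts named there. Protocol 8.1 sets the same restriction.

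The response endpoints rest on that set:
- ORR (SAP 3.4.3): "The point estimates of ORR along with the exact Clopper-Pearson 95% CI will be presented by treatment arm in the Monotherapy Dose Expansion part", on the Efficacy Population.
- BOR (SAP 3.4.4.2): the Efficacy Population. The categories in SAP 3.4.1 end with "Progressive Disease (PD), and Not Evaluable (NE) for patients with measurable disease".
- DCR (SAP 3.4.2.2): "Disease control rate (DCR) per RECIST is defined as the proportion of patients whose best overall response is CR, PR, or SD", with stable disease lasting at least 4 weeks from first dose. SAP 3.4.4.3 adds "DCR per RECIST v1.1 and iDCR per iRECIST will be analyzed in same manner as ORR".

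The time-to-event endpoints do not. SAP 3.4.4.5 states "PFS/iPFS summaries will be presented based on Safety Population" and SAP 3.4.4.6 states "OS summary will be presented based on Safety Population". The Safety Population is everyone given at least one full or partial dose. Table 3-3 has a PFS row for patients described as "Alive with No (or Non-evaluable) post-baseline disease assessments", who are censored at first dose.

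SAP 3.3.1 will summarise the size of each analysis population and the reasons for exclusion, in total. SAP section 5 records 0 responses across the two monotherapy arms. No ORR, BOR or DCR on all treated patients is planned.

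**The concern.** Having a post-baseline scan is itself an outcome. A patient who dies, deteriorates or withdraws before the first scan is missing from the response tables for a reason that is probably unfavourable, and cannot be in the numerator of ORR or DCR. Removing that patient can push a non-zero rate up and cannot push it down. BOR already has a not-evaluable category, but a treated patient with no assessment never reaches that table.

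DCR is where this could matter. With 0 responses, the ORR point estimate cannot move. SAP 2.2.4 says that an arm with no responses might still show benefit by other means, naming durable stable disease, so readers may look to DCR for signs of activity. DCR is also the rate whose point estimate the exclusion can inflate. For ORR the effect is on the interval only: fewer patients give a higher upper limit.

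**Working it through.** **Inputs.** Part 1 plans at most 15 treated patients per arm and 30 overall (SAP 2.2.4). Responses are 0 (SAP section 5). The interval is Clopper-Pearson 95% (SAP 3.4.3). The number treated (N) and the number excluded (m) are not in the documents. N = 30, N = 24, the values of m and the example of 8 disease-controlled patients are my assumptions.

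**The plan's own figures.** With a uniform prior and 0 of n responses, the posterior is Beta(1, n+1). Its mean is 1/(n+2), and its 5th and 95th percentiles are 1 − 0.95^(1/(n+1)) and 1 − 0.05^(1/(n+1)).
- n = 15: mean 1/17 = 5.9%, 90% interval 0.3% to 17.1%.
- n = 30: mean 1/32 = 3.1%, 90% interval 0.2% to 9.2%.

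Both match SAP 2.2.4.

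**ORR upper limit.** For 0 of n, the Clopper-Pearson 95% upper limit is 1 − 0.025^(1/n).

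**DCR.** With x disease-controlled patients, the all-treated rate is x/N and the planned rate is x/(N − m). Their ratio is N/(N − m), whatever x is, provided x > 0.

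| Setting (assumed) | Excluded | Patients analysed | ORR 95% upper limit | DCR multiplied by |
|---|---|---|---|---|
| Overall, N = 30 | 0 | 30 | 11.6% | 1.00 |
| | 1 | 29 | 11.9% | 30/29 = 1.03 |
| | 2 | 28 | 12.3% | 30/28 = 1.07 |
| | 4 | 26 | 13.2% | 30/26 = 1.15 |
| One arm, N = 15 | 0 | 15 | 21.8% | 1.00 |
| | 1 | 14 | 23.2% | 15/14 = 1.07 |
| | 2 | 13 | 24.7% | 15/13 = 1.15 |

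If only 24 were treated overall, the ORR limit is 14.2% with none excluded, 14.8% with one and 16.8% with four.

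DCR example with 8 controlled: 8/30 = 26.7%, 8/29 = 27.6%, 8/26 = 30.8%.

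**How large m might be.** The only related figure is in protocol 1.3.4: 33 of 34 patients were evaluable for response in ANV419-001. Taking 1/34 as the rate for 30 treated, the binomial gives P(m = 0) = 41%, P(m ≤ 1) = 78% and P(m ≥ 4) = 1%. Allowing for uncertainty in that rate (uniform prior updated with 1 of 34, beta-binomial), these become 29%, 56% and 13%. This is only a rough guide: it rests on one patient in a mixed-tumour study that was still running, and the visible text does not say why that patient was not evaluable. It suggests that none or one is most likely and that four is a high-end case.

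**The case against.** The restriction is prespecified in the protocol, and the SAP follows it for ORR, BOR and DCR. The SAP is dated 08 July 2024, after the stop on 27 February 2024, so a new analysis set would be chosen with the 0 responses known. Summaries are descriptive, with no formal testing. Population sizes and exclusion reasons will be reported, denominators defined and tumour data listed, so a reader could divide the reported count by the Safety Population total. Only one post-baseline assessment is needed, and disease evaluation is sought at the End of Study visit, so few patients should be lost.

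The contrast with PFS is also weaker than it looks. Living patients with no assessment are censored at first dose and add nothing to the curve afterwards; the difference has substance for OS and for early deaths.

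All of this stands, and it limits the point to a minor one. It does not remove the upward effect on DCR or the wider ORR interval when anyone is excluded. Nor does the post hoc timing favour the drug, because an all-treated analysis cannot raise DCR or the ORR upper limit. An all-treated efficacy set is not foreign to this plan either: the SAP uses one for PFS and OS although protocol 8.2.4 assigns efficacy analysis to the Efficacy Population, a change that section 5 does not list.

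**Conclusion.** The point holds, conditionally. If every treated patient had a post-baseline assessment, there is no effect. Otherwise DCR is overstated by the factor N/(N − m) when anyone is disease-controlled, and the 0-response upper limit rises. With 30 treated and one excluded, the effect is small: 11.6% to 11.9% for the limit and a factor of 1.03 for DCR. Within an arm of 15, two exclusions give 21.8% to 24.7% and a factor of 1.15. These sizes rest on the assumed N and m. The direction rests only on the fact that an unassessed patient cannot enter the numerator. The 0% ORR and the Part 1 stop do not change.

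**What to change.** Report ORR, BOR and DCR per RECIST on the Safety Population as well. Count treated patients with no post-baseline assessment as not evaluable for BOR, as non-responders for ORR and as not disease-controlled for DCR. Keep the protocol's Efficacy Population result alongside. Add to the disposition table in SAP 3.3.1 an explicit count, by arm, of treated patients excluded from the Efficacy Population. Record the addition in SAP section 5, or in the CSR if the database is already locked, and say there that it was made after the 0 responses were known.

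The cost is one repeated table, one added row and a few lines of text. DCR may come out slightly lower. In return, the response rates are available on the same patients as PFS and OS.
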